#### **Time to first improvement through Day 33 where recovery is defined as a clinical status of 1 or 2**

Time to recovery is defined as (first date of clinical status improvement [defined as a 1-point or more decrease in scale from baseline] – randomization date + 1). Subjects which do not have this event, or who are considered failures based on clinical status imputation methods corresponding to the primary analysis, will be considered censored at Day 33.

#### **Length of hospital stay (time to discharge) through Day 33**

Length of hospitalization is defined as (date of discharge [event] – randomization date + 1). Subjects which do not have this event will be considered censored at Day 33. Only the index hospitalization will contribute to this endpoint; readmittance will not be considered for analysis, but these incidences will be provided in data listing. Additional event (hospital discharge) and censoring (no hospital discharge) details are included in a subsequent section.

#### **Cumulative duration of IMV through Day 33**

Cumulative duration on IMV through Day 33 and is defined as (IMV end date – IMV start date + 1). If a subject was repeatedly put on IMV on the same day, the study day will only be counted once. If a subject was placed on IMV more than once, the cumulative duration will reflect the total number of days on ventilation (e.g. sum of each IMV end date – IMV start date + 1).

#### **Proportion of subjects requiring IMV through Day 33**

This is defined as the proportion of subjects who had IMV in the period from date of randomization to Day 33. If a subject has two or more events during this time, (s)he will still be counted only once.

#### **Proportion of subjects with severe progression defined as requiring ECMO, IMV and/or have died through Day 33**

This is defined as the proportion of subjects who had any of these progressive events in the period from the date of randomization to Day 33. If a subject has two or more events during this time, (s)he will still be counted only once.

### **Length of time in ICU through Day 33**

Length of time in ICU includes number of days spent in the ICU from randomization through Day 33 and is defined as [ICU discharge date – (later of ICU admittance date, randomization date) + 1]. If a subject was discharged and readmitted to the ICU on the same day after randomization, the study day will only be counted once. If a subject was admitted to the ICU more than once, the length of time in ICU will reflect the total number of days on ventilation [e.g. sum of each ICU discharge date – (later of IMV admittance date, randomization date) + 1].

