Cumulative duration in ICU will be imputed similarly, unless a patient has a useable discharge date (e.g. not occurring prior to prohibited medication use); in this case, the ICU discharge date will be set to the hospital discharge date. If a subject's last assessment identifies that IMV was used (and has no usable end date), the date on which it is no longer used will be assumed Day 33 unless the subject is discharged from the hospital prior to Day 33. If this occurs, the hospital discharge date will be used. IMV end dates will be imputed similarly, assuming that IMV ceases at the time of ICU discharge. Hospitalization, ICU, and IMV end dates for subjects who died prior to Day 33 during these events (e.g. after ICU admission or IMV initiation) will result in assumed end dates of Day 33 for endpoint analyses, so long as prohibited medication was not administered. Any dates on or after the start date of prohibited medication use will be considered unusable for imputation purposes; ongoing hospitalization, ICU, or IMV at the time of medication use will default to extrapolation to Day 33.

For the key secondary endpoint involving severe progression (ECMO, IMV, and death), subjects who withdrew early from study prior to Day 33 without evidence of events will be treated as not having the event. Sensitivity analyses will be conducted (1) treating them as failures (having the event at their last study visit) and (2) excluding them from the analyses. An additional analysis of these endpoints will be provided, treating prohibited medication use prior to Day 33 as an event, as well as allowing for status (event or success) without regard to prohibited medication use.

The outcomes for safety assessment and for additional efficacy analysis as well as exploratory endpoints will not be imputed if data is missing.

Please also refer to the more detailed descriptions in sections 12 to 18 of this SAP for additional details on the handling of missing data for particular endpoints and analyses.

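### The SAP's only rule for repeat ICU stays counts ventilation days instead of ICU days, and one example of a usable discharge date in SAP 4.1 is inverted

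*SAP*

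**What the plan says.** **Single stay.** SAP 12, under Length of time in ICU through Day 33, opens with the right concept: "Length of time in ICU includes number of days spent in the ICU from randomization through Day 33". The interval ends at ICU discharge and starts at the "later of ICU admittance date, randomization date) + 1". SAP 14 and Protocol 9.2.3.2 give the same single-stay formula.

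**More than one stay.** The same SAP 12 definition then says that "the length of time in ICU will reflect the total number of days on ventilation". Its bracketed formula sums intervals that end at ICU discharge but start at the "later of IMV admittance date, randomization date) + 1". Neither SAP 14 nor Protocol 9.2.3.2 has a formula for repeat stays, so this is the only one in the documents.

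**Usable dates.** SAP 4.1 extrapolates an ICU stay without an end date to Day 33, "unless a patient has a useable discharge date (e.g. not occurring prior to prohibited medication use"; where such a date exists, the hospital discharge date is used as the ICU end date. Later, SAP 4.1 states the rule outright: "Any dates on or after the start date of prohibited medication use will be considered unusable for imputation purposes". For length of hospitalization, SAP 4.1 likewise does not count a discharge on or after the start of prohibited medication as an event.

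**Role of the endpoint.** SAP 14 tests ICU time fifth of six key secondary endpoints, at two-sided 0.05, with a van Elteren test stratified by age category and baseline ICU status. Mortality is tested sixth, and testing stops at the first non-significant result.

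**The concern.** The repeat-stay sentence describes a different quantity from the endpoint it belongs to. Days in the ICU and days on a ventilator coincide only if the subject is ventilated for the whole of every stay. Repeat stays are clearly foreseen: SAP 12 deals with discharge and readmission on the same day, and SAP 14 counts returning as well as new ICU admissions for another secondary endpoint.

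A program that follows the sentence would undercount some readmitted subjects and would have to improvise for any stay without IMV. The test is rank-based, so a subject moved from a long to a short duration changes rank. If testing reaches this endpoint, its result also decides whether mortality is tested.

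The example in SAP 4.1 is a smaller matter. Read literally, it accepts exactly the dates that the later rule rejects. SAP 14 relies on usable ICU end dates without defining them, so a programmer would look to SAP 4.1 for the meaning.

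**Working it through.** The documents give no figure for ICU time, so there is none to reproduce. The check sets the rules side by side and applies them to assumed subjects. Randomization is on Day 1.

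**1. Repeat stays.** Assumed subject A has an ICU stay on Days 3–10 with IMV on Days 6–9, and a second ICU stay on Days 15–20 without IMV.

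- ICU dates for every stay (end − start + 1): (10 − 3 + 1) + (20 − 15 + 1) = 8 + 6 = **14 days**.
- The sentence, days on ventilation: 9 − 6 + 1 = **4 days**.
- The bracketed formula, with the IMV admittance date assumed to mean the start of IMV: 10 − 6 + 1 = **5 days** for the first stay. The second stay has no IMV date, so its term is **undefined**.

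The sentence therefore disagrees both with the endpoint and with its own formula. Its wording matches the definition of cumulative IMV duration in SAP 12, where "the cumulative duration will reflect the total number of days on ventilation" is correct. It was probably carried over from there.

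**2. Usable discharge date.** Assumed subject B enters the ICU on Day 3, has no ICU end date, and starts prohibited medication on Day 10. If the hospital discharge date is usable, ICU time is discharge day − 3 + 1. If not, it is 33 − 3 + 1 = 31.

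| Hospital discharge | Explicit rule in SAP 4.1 | Example read literally |
|---|---|---|
| Day 8 (before the medication) | usable: 8 − 3 + 1 = 6 days | not usable: 31 days |
| Day 20 (after the medication) | not usable: 31 days | usable: 20 − 3 + 1 = 18 days |

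The two readings give opposite handling in both rows. For this slip to matter, a subject must meet four conditions together: an ICU stay, no usable ICU end date, a hospital discharge date, and prohibited medication use.

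**3. Check on the repair.** Replacing IMV with ICU in the bracket is not quite enough. For an ICU stay that ended on Day 0, the start becomes Day 1 and the term is 0 − 1 + 1 = 0. For one that ended a day earlier, it is −1 − 1 + 1 = −1, which would be subtracted from later stays. The sum has to be limited to stays that overlap randomization through Day 33.

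**The case against.** The best reply is that the intent can be recovered. The opening sentence of the definition covers days in the ICU without limiting them to one stay. The same-day readmission rule also counts ICU days. SAP 20 records no departure from the protocol, so no switch to ventilation days was meant. The IMV admittance date is not a term used elsewhere (the IMV definition speaks of a start date), so a careful programmer would more likely raise a query than compute the wrong number. SAP 4.1 settles usability by an explicit rule, against which the example is only a parenthesis. SAP 7 also provides a blinded review at which imputations are finalized. Finally, ICU time is tested only if the primary and four earlier key secondary endpoints are all significant.

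Most of this stands, and it limits the point. Two stronger inferences are tempting but unsupported. A reader might conclude that the ICU endpoint as a whole is misdefined. It is not: the single-stay definition is right in SAP 12, SAP 14 and Protocol 9.2.3.2. A reader might also conclude that every prohibited-medication user would be imputed the wrong way. The explicit rule in SAP 4.1 governs, and only subjects who meet all four conditions could be touched.

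The reply does not remove the need for a correction. The only repeat-stay formula for a confirmatory endpoint is wrong as written, and blinded review should apply an endpoint definition, not have to repair one.

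**Conclusion.** The point holds in a narrow form. The repeat-stay rule in SAP 12 is wrong as written for subjects with more than one ICU stay. For assumed subject A it gives 4 days, or 5 plus an undefined term, against 14. The 5-day figure rests on reading the IMV admittance date as the start of IMV. The example in SAP 4.1 contradicts the section's own rule, and for assumed subject B it changes the duration from 6 to 31 days or from 31 to 18. Both look like drafting slips.

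The example subjects only illustrate the rules. The documents do not say how many subjects have repeat ICU stays, or how many meet the four conditions in SAP 4.1. The effect on the treatment comparison is therefore unknown, and no bias in either direction is shown. No sample size, power or alpha figure changes. The correction is worth making because the endpoint is confirmatory and stands directly before mortality in the testing order.

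**What to change.** Make two wording changes in the SAP, documented before unblinding.

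1. **SAP 12, Length of time in ICU.** For subjects with more than one stay, define the result as the total number of days in the ICU: the sum of (end − start + 1) over all ICU stays that overlap the period from randomization through Day 33. The end is ICU discharge, or Day 33 if that is earlier. The start is ICU admission, or randomization if that is later. Each study day counts once. This removes both the reference to ventilation and the undefined "later of IMV admittance date, randomization date".
2. **SAP 4.1.** Turn the example round, so that a usable discharge date is, for example, one occurring before the start of prohibited medication. Keep it as an example, because SAP 14 also names withdrawal as a reason for lacking a usable end date.

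The cost is two phrases and a check that the program follows them. No new data, no change of test and no change to the hierarchy are needed.

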### **Proportion of subjects admitted to the ICU from randomization through Day 33**

This is defined as the proportion of subjects who were admitted to the ICU in the period from the date of randomization to Day 33. If a subject has two or more events during this time, (s)he will still be counted only once.

### **Mortality rate through Day 33**

This is defined as the proportion of subjects who died in the period from the date of randomization to Day 33.

### **Proportion of Subjects who are Tested as “Not Detected” on Day 7**

This is defined as the proportion of subjects with “not detected” result for SARS-CoV-2 from an rRT-PCR test on Day 7. If the subject has multiple measurements on the same study day, the last measurement will be used.

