3.1.2.2 Other Secondary Efficacy Endpoints

- Results of reverse transcription polymerase chain reaction (RT-PCR) for SARS-CoV-2 from nares/throat swab and/or sputum and/or lower respiratory tract sample on Day 7.
- Proportion of subjects admitted to the ICU from randomization through Day 33
- Proportion of subjects with improvement on Days 7, 14, 21, and 33
- Proportion of subjects requiring IMV by Day 33
- Time to recovery through Day 33 where recovery is defined as a clinical status of 1 or 2
- Time to first improvement in clinical status through Day 33

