6.1.3 Endpoint Visit 5 (Day 7)

The following assessments will be performed 3 days after the end of daily infusions (Day 7 or on day of discharge if prior to Day 6 and restrictions prevent inpatient Day 7 visit and not already performed as part of the assessments for that day):

1. Vital signs
2. SpO₂ saturation and A-a Gradient (see Section 7.2.4) (for subjects discharged prior to Day 6, telephone contact will be made with the subject on Day 7 to ascertain SpO₂)
3. Swab for RT-PCR detection of SARS-CoV-2 to determine infection status
4. Clinical Status and Oxygenation/Ventilator Status Evaluation

5. Modified Borg Dyspnea Scale
6. MQoL-SIS
7. Chest CT/Chest X-ray
8. Blood sampling for clinical laboratory evaluations (specified in Section 7.3.4)
9. AE monitoring
10. Concomitant medication use

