7.2.3 Viral Clearance

COVID-19 infection status will be re-assessed on Day 7 using an RT-PCR assay to evaluate viral clearance. A nares/throat swab and/or sputum and/or lower respiratory tract sample will be taken for the assessment. If the initial Day 7 RT-PCR test is negative, a repeat test will be performed as soon as possible and no later than at the Day 14 visit.

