#### **4.6 Reporting Timeframe of Measurement for Analysis**

For analyses of primary and secondary efficacy endpoints, including clinical status and RT-PCR, the latest observation within any given study day will be used. If the observations for the Day 7 visit falls outside of the 24-hour window of the study day or the Day 14 visit falls outside of the 48-hour window of the study day, the observation will be considered as missing and the imputation described in Section 4.1 will apply as appropriate. Otherwise, unless specifically stated otherwise, analyses will be conducted based on nominal visits.

For summary analyses of efficacy assessment, including oxygenation, oxygen saturation, modified Borg Dyspnea Scale and McGill Quality of Life Single-Item Scale (MQoL-SIS) and safety parameters (including vital signs, clinical laboratory evaluations and chest CT/chest X-ray findings), the latest observation within the study day during treatment period will be used. No imputation will be made for these assessments.

For safety analysis with adverse events, the observation with highest severity within the study day during treatment period will be used. No imputation will be made.

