## 10. Summary of Subject Assessment

The following assessments will be summarized:

- Demographics and Baseline Characteristics (ITT population, Safety Population, and Per Protocol Population)  
Baseline demographic and characteristics (e.g. age, gender, height, weight, race, ethnicity)
- Medical History (ITT population, Safety Population, and Per Protocol Population)  
Medical history data by Medical Dictionary for Regulatory Activities (MedDRA) System Organ Class and Preferred Terms.
- Physical Examinations, Vital Signs, Weight, Oxygen Saturation (SpO2), Laboratory Results (Safety Population)  
Physical exam, vital signs, weight, SpO2, spirometry and laboratory results including chemistry and hematology, will be summarized by visit.
- Clinical Status and Oxygen/Ventilator Status (ITT population and Safety Population)  
The clinical status and ventilator status will be tabulated according to the categories defined in the protocol by visit, regardless of prohibited medication use, based on shifts from baseline displays. Additional summaries may be provided, suppressing information following prohibited medication use, if use of prohibited medications is highly prevalent.
- rRT-PCR (ITT population)  
The result of rRT-PCR will be tabulated according to predefined categories by visit and sample type.
- Chest X-ray (Safety Population)  
The assessment of pulmonary infiltrate and pleural effusion over time will be tabulated separately for pre-specified age strata and visit.

- Borg Dyspnea Scale and McGill Quality of Life Single Item Scale (ITT Population)

The scale measures will be summarized by descriptive statistics by visit.

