Mortality rate is defined as the proportion of subjects who have died on or prior to Day 33. For this analysis, subjects who use prohibited medication prior to the earliest of death or Day 33 will not be included in analyses. Hypothesis testing will be performed as described for the primary endpoint.

Key secondary endpoints which demonstrate statistical significance will be analyzed by subgroups including sex (male/female), race, ethnicity, geographic region, and disease severity (according to the definitions in the eCRF). All key secondary endpoints will be analyzed by age using testing analogous (unstratified) testing methodology to the specified analyses. Length of time in ICU from randomization through Day 33 will also be analyzed by baseline ICU status. Sensitivity analyses, using all available data, regardless of prohibited medication usage, will be conducted where applicable. The descriptive analyses for the following other secondary endpoints will be based on the primary efficacy analysis (e.g. CMH) method:

- Proportion of patients whose results of reverse transcription polymerase chain reaction (RT-PCR) for SARS-CoV-2 from nares/throat swab and/or sputum and/or lower respiratory tract sample are “Not Detected” on Day 7
- Proportion of subjects admitted to the ICU from randomization through Day 33
  - Only admittance (new or returning) post-randomization will qualify as an event
  - Analyses will be stratified additionally by baseline ICU status
  - If expected event counts do not satisfy CMH testing criteria, baseline ICU status will be removed from analysis as a first step in analysis update
- Proportion of subjects with improvement on Days 7, 14, 21, 33

- Proportion of subjects requiring IMV by Day 33.

The descriptive analyses for the following, other secondary endpoints will be based on the Kaplan-Meier analysis of length of hospitalization:

- Time to recovery through Day 33 where recovery is defined as a clinical status of 1 or 2
- Time to first improvement in clinical status through Day 33

These secondary endpoints will also be analyzed by age category.

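### Day 7 viral clearance is scored on the last RT-PCR of the day whatever the specimen, so a same-day positive can be discarded; a minor point, fixed by an any-positive rule

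*SAP*

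**What the plan says.** - **Endpoint.** Protocol 3.1.2.2 lists the RT-PCR result from a "nares/throat swab and/or sputum and/or lower respiratory tract sample on Day 7". SAP 12 defines the measure as the "proportion of subjects with “not detected” result for SARS-CoV-2 from an rRT-PCR test on Day 7", without naming a specimen.
- **Several results on one day.** SAP 12: "If the subject has multiple measurements on the same study day, the last measurement will be used". SAP 4.6, in a sentence that names RT-PCR, says that "the latest observation within any given study day will be used".
- **Specimens.** Protocol 7.2.3: "A nares/throat swab and/or sputum and/or lower respiratory tract sample will be taken for the assessment". The Day 7 visit list in Protocol 6.1.3 is narrower: "Swab for RT-PCR detection of SARS-CoV-2 to determine infection status". The synopsis for that visit also mentions only a swab.
- **Repeat test.** Protocol 7.2.3 requires a further test when the first Day 7 result is negative, by the Day 14 visit at the latest. The SAP does not say how that result is used.
- **Analysis.** SAP 14 puts all specimen types into one proportion, based on the CMH method of the primary analysis. It calls the analysis descriptive, and the endpoint is not one of the six in the hierarchy.
- **Display.** Under SAP 10, RT-PCR results are "tabulated according to predefined categories by visit and sample type".

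**The concern.** A rule that picks the last result by time works when repeated measurements are interchangeable. Specimens from different parts of the airway need not be. If virus is found in one Day 7 specimen and a later specimen that day is negative, the rule counts the subject as cleared on a day when virus was detected.

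This also fits poorly with Protocol 7.2.3, which does not treat one negative as conclusive, since it asks for a repeat. At stake is the meaning of the Day 7 clearance proportion, which serves a stated secondary objective. The primary result is not affected.

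**Working it through.** The documents give no clearance rate, assay sensitivity, specimen mix or power for this endpoint, so there is no planned figure to reproduce. The check compares the two scoring rules and then adds an illustration from assumed inputs.

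**1. The two rules side by side, for two specimens on Day 7**

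| Earlier | Later | Last-value rule (SAP 12, 4.6) | Any-positive rule |
|---|---|---|---|
| positive | positive | Detected | Detected |
| negative | negative | Not Detected | Not Detected |
| negative | positive | Detected | Detected |
| positive | negative | **Not Detected** | **Detected** |

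The rules differ only in the last row. With more than two specimens they differ only when the last is negative and some earlier one is positive. So the last-value rule can raise the Not Detected proportion relative to any-positive, and can never lower it.

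**2. Can the last row occur?** It needs at least two Day 7 results. Protocol 7.2.3 permits several specimens, but Protocol 6.1.3 schedules one swab. The only repeat that the protocol requires follows a negative, and so cannot by itself produce positive-then-negative. The sequence is permitted but not planned.

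**3. Effect for one affected subject (assumed sensitivities).** Take a subject who is still infected, sampled at both sites, with the swab last. Assume a swab sensitivity of 60–80%, a lower-airway sensitivity of 90% and independent errors.
- Last-value: P(called clear) = 1 − swab sensitivity = 1 − 0.80 to 1 − 0.60 = 20% to 40%.
- Any-positive: P(called clear) = (1 − swab sensitivity) × (1 − 0.90) = 0.20 × 0.10 to 0.40 × 0.10 = 2% to 4%.

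**4. Effect on the whole endpoint (assumed frequencies)**

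Shift = q × d × l, where
- q = share of subjects with both specimens on Day 7, assumed 5–20%;
- d = share of those who are lower-airway positive and swab negative, assumed 10–30%;
- l = probability that the swab is the later specimen, assumed 50–100%.

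Low: 0.05 × 0.10 × 0.50 = 0.0025, or 0.25 points; 104 × 0.0025 = 0.26 subject per arm of 104.

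High: 0.20 × 0.30 × 1.00 = 0.06, or 6.0 points; 104 × 0.06 = 6.24 subjects per arm.

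If no subject has two Day 7 specimens, the shift is zero. If the shift is equal in both arms, the between-arm difference does not move.

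**The case against.** The strongest case against runs as follows. The visit schedule asks for one swab, so multiple specimens are the exception. The rule is symmetric in form, since a later positive also replaces an earlier negative. It applies equally to both arms. The endpoint is descriptive, the SAP 10 tabulation will show results by specimen, and the blinded review in SAP 7 may settle individual data points.

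Most of this stands, and it limits the size and importance of the point. The symmetry argument does not: a later positive gives the same score under either rule, so the departure from any-positive runs one way only. The tabulation shows the specimens but does not change how the endpoint is scored. A case-by-case decision at blinded review is no substitute for a written rule.

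A reader might infer more: that lower-airway samples come mainly from ventilated subjects, so that a treatment effect on ventilation would create a clearance difference between arms with no virological effect. The documents do not support this. They do not say how the specimen is chosen, do not link the choice to the subject's condition, and name a swab in the visit list. As pure assumption, the difference would be true persistence × gap between arms in lower-airway sampling × gap in sensitivity. This runs from 0.50 × 0.05 × 0.10 = 0.25 points to 0.90 × 0.20 × 0.30 = 5.4 points. Any such dependence should be labelled an assumption.

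A reader might also conclude that the comparison should rest on swabs alone. That would drop subjects who have only another specimen, a selection made after randomization and at odds with the ITT basis in SAP 14.

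**Conclusion.** The point holds as a minor one. As written, the SAP lets a later negative override an earlier positive from the same day, whatever the specimens. Against an any-positive rule, this can only raise the Not Detected proportion.

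The size is unknown. It is zero if nobody has two Day 7 specimens, and 0.25 to 6.0 points under the frequencies assumed above. That the direction is one-sided follows from the text of the rule alone; the range rests entirely on assumption. The primary and key secondary tests, the type I error and the sample size are untouched.

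Two gaps in the text belong to the same point: the repeat test has no stated role in the endpoint, and the protocol names a swab in one place and three specimen types in another.

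**What to change.** 1. In SAP 12 and SAP 4.6, score a subject Detected if any Day 7 specimen is positive, and Not Detected only if all Day 7 specimens are negative.
2. State how the repeat test of Protocol 7.2.3 enters the endpoint. A same-day repeat would fall under item 1; a repeat on a later day needs its own sentence.
3. Reconcile Protocol 6.1.3 and the synopsis (swab) with Protocol 7.2.3 and 3.1.2.2 (three specimen types).
4. Keep all ITT subjects with a Day 7 result in the main comparison. Show swab-only results as a supportive display, drawn from the SAP 10 tabulation by sample type.

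The cost is a few sentences and one supportive display, with no new data collection. The small downside is that subjects with more specimens have more chances to be scored Detected, so the number of Day 7 specimens per subject should be reported by arm.
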